35.0 Surveys and Questionnaires

35.1 *Does the project involve the use of Surveys, Questionnaires or Interviews?

Yes No

36.0 Surveys and Questionnaires Detail

36.1 *Will subjects be identified in any way?

Yes No

37.0 Study Population

37.1 *Briefly describe your targeted population. (Patients with a condition or disease, healthy control subjects, etc.)

We are looking to recruit 50 paid, non-treatment-seeking male and female volunteers with alcohol use disorder (AUD) of greater than or equal to moderate severity.

37.2 *Explain rationale for using human subjects.

The purpose of this study is to evaluate the efficacy of CORT118335 as a potential treatment for alcohol use disorder of greater than or equal to moderate severity; therefore, use of humans is essential to determining the efficacy of CORT118335 as a potential treatment in this disorder.

37.3 *Age

Age Range Not Applicable

Enter the specific age range for study population.

From:

18

To:

75

37.4 *Gender

- Male
- Female
- Both male and female

37.5 *How many subjects are you planning to enroll at this institution/site?

50

If this is a chart review, indicate the number of charts: (If this is not a chart review, enter 0.)

N/A

If necessary, provide explanation below.

37.6 *How many subjects will be enrolled at ALL sites? (Include Scripps and NON-Scripps)

50

If necessary, provide explanation below.

37.7 To achieve your needed number of subjects, how many subjects do you estimate will need to give informed consent? (Allowing for screen failures)

100

37.8 *Justification for the number of subjects required:

Previous studies in our lab have shown that we need to give informed consent to 100 subjects in order to enroll the 50 subjects required for the study.

37.9 Please check all potentially vulnerable populations that are included:

* Regulated

- Children / Minors (subjects less than 18 years) *
- Pregnant Women *
- Prisoners *
- Economically or educationally disadvantaged persons
- Non-ENGLISH speaking

- Diminished mental capacity
- Physically disabled
- Students
- Scripps Health Employees
- Scripps Research Institute Employees
- Other

If other, describe.

If including vulnerable subjects, explain why. Explain what safeguards are included to protect against coercion or undue influence.

37.10 Inclusion Criteria

*Use the link below to add inclusion criteria.

Order Number	Criteria
1	
 • Male or female volunteers, 18-75 years of age. • Meets DSM-5 criteria for current alcohol use disorder of moderate or greater severity (AUD-MS, ≥ 4 symptoms). • In the month prior to screening, reports drinking ≥ 21 standard drinks per week if male, ≥ 14 if female, with at least one heavy drinking day (≥ 5 drinks/d if male, ≥ 4 drinks/d if female) per week. • Subjects will be non treatment-seekers because the study is not a treatment trial, and to avoid exposing treatment-seekers to alcohol cues. • Subjects must be abstinent a minimum of 3 days (but not more than 7 days) prior to the alcohol cue reactivity lab session. • Negative BAC and EtG/EtS and a CIWA score of ≤ 9 at the time of the lab session. • In acceptable health in the judgment of the study physician, on the basis of interview, medical history, physical exam, ECG, routine urine and blood chemistry. • Females with childbearing potential must have a negative pregnancy test on the screening and randomization visits. • All subjects must agree to use double barrier contraception for the duration of the study and one month thereafter, i.e., males must use condoms and females must use spermicide and/or a non hormonal barrier method, and their opposite sex partner must likewise use an effective non hormonal form of contraception. • Able to provide informed consent and understand questionnaires and study procedures in English. • Willing to comply with the provisions of the protocol and take oral medication.

37.11 Exclusion Criteria

*Use the link below to add exclusion criteria.

Order Number	Criteria
--------------	----------

1

- Medical conditions that could be aggravated by glucocorticoid and/or mineralocorticoid antagonism, such as: autoimmune disease, hypotension, or postural hypotension.
- Clinically significant findings on physical exam, ECG, urine or blood tests that may increase risk, e.g., serum potassium outside of the normal range.
- Meets DSM-5 criteria for a current major psychiatric disorder, including mood, anxiety or substance use disorders, other than alcohol, nicotine, or mild cannabis use disorders. However, subjects with a history of depression, who have been on a stable dose of anti-depressant medication for at least 3 months, and do not meet DSM-5 criteria for current depression or anxiety disorders may be admitted.
- Has an ACQ total score of ≤ 30 and/or is non cue reactive., i.e., VAS craving severity score < 3 points higher to alcohol cues than to water cues, at Visit 1 (screening).
- Cannot provide a urine drug screen negative for substances of abuse other than alcohol or cannabis.
- Liver function tests more than 3 times the upper limit of normal or elevated bilirubin.
- Pregnant or lactating.
- Treatment within the month prior to screening with (1) an investigational drug, (2) drugs which may negatively interact with study medications, or (3) drugs that may influence study outcomes (e.g., disulfiram [Antabuse], naltrexone [ReVia], acamprosate [Campral], or anticonvulsants.
- Chronic systemic steroid use
- Using drugs that are strong inhibitors and inducers of CYP2C9.
- No fixed domicile and/or no availability by home or mobile telephone.

37.12 Provide justification for inclusion or exclusion of any group (gender, race, ethnicity or other):

All gender, race and ethnicity groups will be included.
Excluded groups include children and pregnant or breast-feeding women.

37.13 Subject Debriefing

Describe any debriefing procedure(s).

Following the cue reactivity procedures, subjects are debriefed and complete rating scales to assure that mood and craving have returned to baseline.

***When will participants be given experimental results and the key to any study blinding? (If not known, request this information from the Sponsor.)**

Once the last randomized subject has completed the study and follow-up visit, the blind will be broken on drug assignment. At that time, subjects requesting the identity of their medication group assignment will be notified as to which group they were in during the study. Results will be available within one year of study completion.

38.0 Nursing, Allied Health and Health Services Research

38.1 *Is this Nursing, Allied Health or Health Services Research ? (Note: Health Services research is the study of the organization, delivery and financing of health care. Some projects of this type may be considered Quality Assurance, Quality Improvement or Process Improvement but NOT research.)

Yes No

39.0 Human Specimens and Cell Lines

39.1 *Will ANY specimens, other than blood, be obtained for this study?

Yes No

40.0 Human Specimens and Cell Lines Detail

40.1 Human Specimens

**With regard to human specimens, check all that apply.*

- Identifiable (patient identifiers (Name, Medical Record Number), Family History (Pedigree), Treatment and Outcome Data)
- Unidentifiable (Demographics (Race, Gender, Age), Diagnosis, Histopathology, Specimen Descriptors (Type, Condition, Amount) - if Yes, may meet criteria for Exempt, Category 4
- Genetic Analysis
- Genomic Analysis
- Proteomic Analysis

40.2 *Specimen Type (Check all that apply)

- Cells
- Stool
- Hair / Nails
- Saliva
- Semen
- Urine
- Tissue
- Fluid
- Bone Marrow Aspirate
- Other

If fluid, tissue or other, describe.

40.3 *Will the specimens come from samples originally obtained for clinical purposes?

Yes No

40.4 If Yes, describe how the samples were obtained and if informed consent was required.

40.5 If No, where will the specimens come from?

The samples will be obtained for research purposes only during a subject's study visit at the lab. Subjects will provide saliva samples, urine samples, and will undergo blood draws all of which will be obtained at the lab. Informed consent will be required before any of the above-referenced procedures are undertaken.

40.6 *Will specimens be maintained in such a way that the subjects can be identified?

Yes No

If Yes, how will confidentiality be preserved?

40.7 *Will specimens be transferred to or from a Scripps Health facility? (If Yes, please complete a Materials Transfer Agreement.)

Yes No

If Yes, how will specimens be identified?

If Yes, to which institution will specimens be transferred?

TSRI

Other:

40.8 *Will this study involve human stem cells? (If 'Yes', attach a copy of the ESCRO approval to the Initial Review Submission Form)

Yes No

If Yes, are the human stem cells derived from human embryonic tissue?

Yes No

If not from embryonic tissue, are the cells pluripotent or capable of being de-differentiated into pluripotent cells?

Yes No

40.9 *Does this study involve established human cell lines?

Yes No

If Yes, name the cell lines:

If Yes, will human cell lines be obtained from a public repository or a public source?

Yes No

Will these cell lines or data be linked directly to the subject from whom they were obtained?

Yes No

40.10 *Will saved samples or their derivatives have the potential to produce profits for the investigators or Scripps?

Yes No

40.11 *Does this study involve the storage of genetic data in electronic form?

Yes No

40.12 *Does this study involve gene transfer or recombinant DNA use in INDIVIDUAL SUBJECTS in a CLINICAL TRIAL?

Yes No

If Yes, then review by an Institutional Biosafety Committee will also be required. To view information on Institutional Biosafety Review of Protocols Involving Gene Transfer Or Recombinant DNA (Appendix M of the NIH Guidelines), click on the Help bubble to the right.

40.13 If Yes, explain.

40.14 *Does the research protocol involve the use of RECOMBINANT DNA TECHNOLOGY or BIOLOGICAL AGENTS or materials that may be infectious in the clinical setting?

Yes No

List infectious agent or rDNA vector.

41.0 Funding Source (If you are a Principal Investigator receiving a Federal funded grant for collaborative sites to conduct Human Subjects Research, contact the IRB office. You will need to submit IRB documents from the collaborating institution.)

IMPORTANT: If ANY funding for this project is coming from a Federal source (federal agency, federal government, National Institutes of Health, National Science Foundation, US military - such as Department of Defense, etc.), the source(s) MUST be entered in this section.

41.1 *Is this study funded by a commercial sponsor?

Yes No

41.2 *Is this study funded by a grant?

Yes No

***Is this an SCMG grant?**

Yes No

If this study is funded by a grant, are you the PI receiving the grant?

Yes No

If you are the PI receiving the grant, will any other projects in the grant use human subjects?

Yes No

**If you are the PI for the entire grant, and checked 'Yes' to 'Human Subjects', please submit a copy of the entire grant.*

41.3 *Status of funding:

Please select one.

Applied/Pending

Approved

Not Applicable

41.4 Sponsor Protocol Number:

N/A

41.5 Grant Number:

P60 AA006420

41.6 *Granting Agency/Sponsor (You can select more than one agency.)
(If your agency is not in the list, click on the help bubble to the right.)

If Departmental Funds are being used, click on 'Private' and choose 'Departmental Funds'.

**Note: All studies must have an identifiable source of funding or they cannot be reviewed. Fill in the matrix below.*

Sponsor	Funding	Protocol Control	Data Coordination	Monitoring	Auditing	Pass Through Funding
Commercial						
Federal or State	NIH	#	0	0	0	0
Private						
CRO						
Department funds						

41.7 Proposed Funding Date - BEGIN

01/01/2018

41.8 Proposed Funding Date - END

12/31/2022

41.9 Are part of or all activities in this proposal funded by a training grant?

Yes No

NCT0446615

Medication Development in Alcoholism: CORT118335 versus Placebo

IRB Summary of Amendments-11/11/2020-04/04/2022

Miricorilant Amendments

Amendment

Submitted on 11/11/20-Approved on 12/09/2020

In obtaining our IND, the FDA requested that we add the following language to our exclusion criteria (Section 37.11 study application):

Based on the in vitro studies conducted for IND 142502, CORT118335 is

- exclusively metabolized by CYP2C19 (94%)
- concentration dependent inducer of CYP3A4 mRNA
- modest inhibitor of CYP3A4 (IC₅₀, 3.9 μM), CYP2C9 (IC₅₀, 5.1 μM) and CYP2C8 (IC₅₀, 7.5 μM)
- potent inhibitor of BCRP (IC₅₀, 0.2 μM) and UGT1A1 (IC₅₀, 1.4 μM).

Given that the in vivo drug-drug interaction of CORT118335 and substrates or inhibitors of CYP enzymes or drug transporters have not been evaluated, in the proposed study, subjects taking substrates of CYP3A4, CYP2C9 and CYP2C8 will be carefully monitored for increased adverse effects of these substrate-drugs and those narrow therapeutic index drugs that are primarily metabolized by these cytochrome enzymes will be excluded.

Thus, subjects will be excluded who are taking:

- strong CYP2C19 inhibitors
- substrates metabolized primarily by CYP3A, CYP2C9 and CYP2C8 with narrow therapeutic index
- BCRP and UGT1A1 substrates

The FDA also asked us to provide criteria that would terminate the study. The following study stopping criteria was added and approved by the FDA:

Criteria to temporarily suspend the study have been established when either of the following specific safety thresholds are met:

- One participant with a Common Terminology Criteria for Adverse Events (CTCAE) Grade 4 treatment related SAE, or
- ≥ 2 participants with a CTCAE Grade 3 treatment related SAE

If the safety threshold is met, the independent Medical Safety Monitor along with a panel of qualified experienced physicians will meet to discuss and assess the severity and relationship of the SAE(s) to CORT118335 and provide a recommendation to the Principal Investigator whether the nature, frequency, and severity of adverse events associated with study treatment warrant the early termination of the study in the best interest of the participants, whether the study should continue as planned, or the study should continue with modifications. Regardless of this decision, FDA will be notified by the Principal Investigator and provided with a summary of the above AEs, as well as the panel's recommendation regarding study continuation and safety monitoring modifications, within 2 days of receipt of the recommendation from the panel.

We have amended the language in the medication supply section of the study application (Section 20.2) from: "The daily dose of six 150 mg tablets will be packaged in wallet cards

provided by Corcept Therapeutics that contain a 2-week supply of double-blind medication, plus a 1-week extra supply for rescheduling purposes if needed" to "The daily dose of six 150 mg tablets will be packaged in wallet cards provided by Corcept Therapeutics. Each wallet card can support 7 days at 900mg/day. Subjects will be provided with 3 wallet cards: 2 cards to support the 2-week dosing duration and 1 additional card to permit rescheduling the cue reactivity testing if necessary. Corcept Therapeutics asked us to make this change for clarification.

We have submitted the study instructions and the study participant information card for approval.

We have partnered with Citrus Labs, a commercial company, to help us with our recruitment efforts for this study. Citrus Labs owns and operates the leading health app network, Mind Mates. Through the Mind Mate app, potential candidates will have already received education on clinical trials (risks, benefits, commitment required, etc.) and requested to participate in a relevant clinical trial. The app will be used to identify, pre-screen (we are requesting approval for the attached pre-screener questionnaire) and refer potential study candidates. The referrals will be delivered via a study dashboard provided by Citrus Labs. We have contracted with Citrus Labs to receive 40 guaranteed referrals.

We will also resume our social media advertising campaign on 12/1/2020 with Dynamic Marketing. Attached are examples of prior social media campaigns (November and December 2019). Since the study procedures and research methods are the same for all of [name] Development for Protracted Abstinence in Alcoholism studies, the attached examples will be updated with minor editorial changes.

Amendment

Submitted on 02/11/21-Approved on 03/15/2021

We received a safety Addendum (1) to the Investigator's Brochure Edition 5 from Corcept Therapeutics and modified the protocol accordingly.

We will obtain an additional blood draw for liver function tests at 9 days after the last dose of medication. Any subject with LFT's that are twice that of baseline and >2X the ULN will be followed to a return to baseline and until the subject is stable.

Subjects will be compensated \$75 for the additional blood draw. The total compensation for the study is \$575.00.

We have amended the name of the study drug from CORT118335 to miricorilant, now that it is being studied in humans under that name.

We request to add the Brief Irritability Test (BITe) to the self-report battery. It is a short 5-item questionnaire to assess irritability and, therefore, administration should not increase subject burden.

The EtG/EtS urine sample in the text of the IFC on page 3 was added to the Visit Schedule on page 4.

Dynamic Marketing will create brief videos (15-30 seconds), in place of written blog posts, advertising the study, or providing useful/helpful information to create interest and drive traffic to our social media posts. We request approval for the two attached videos for February.

We request approval for proposed Dynamic Marketing February social media content that is attached.

We request approval for the attached wallet card that will be given to subjects in case of suspected excess glucocorticoid blockade.

We request approval for Scripps Research COVID-19 procedures that have been added to a subject's email confirmation and driving directions and COVID screening questions to be administered prior to coming to the campus. Language was developed with and approved by Scripps Research's legal department.

Minor editorial changes were made to the IFC (removed abbreviations,) to foster readability and clarity for subjects.

We request approval to have subjects come to our lab, instead of going to Lab Corp, for the blood draw that takes place nine (9) days (plus or minus 2 days) after their Visit 3. Due to prior COVID restrictions, we scheduled this visit off campus. Now that Scripps Research has eliminated visitor COVID restrictions, scheduling subjects at our lab will allow us more control in obtaining this blood collection in the time period (7-11 days after Visit 3) window. We added this as a Visit 4 in the schedule of procedures and will also obtain Vitals as we do for all subject visits. The virtual follow up visit with the study physician is now changed to Visit 5.

Updated enrolled subjects and minor editorial changes (spacing) were also made to the informed consent.

We had 13 other IRB amendments/approvals for recruitment advertisements and administrative issues such as staff changes.

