- No information will be released to non-study personnel regarding the identity or progress of

subjects without written request by the individual subject to the P.I.

- Electronic datasets will be password protected and accessible only to authorized personnel.

Collection and Reporting of AEs and SAEs

The P.I. will be responsible for monitoring the conduct of this single-site human laboratory study to ensure the safety of participants. The P.I. will monitor subject side effect complaints, clinically significant lab abnormalities and findings on physical exam in consultation with study physicians and [name], MD, Pharm D, our Independent Medical Safety Monitor, who has over two decades of experience as a Research Physician in the pharmaceutical industry involved in Phase I, II and III clinical trials. If a SAE occurs, the P.I., in consultation with the Study Physician, [name]., Ph.D., and the Independent Clinical Safety Monitor, [name]., PharmD., will report it to the Scripps-IRB, our NIAAA Project Officer and the US FDA within 48 hours of becoming aware of the event. The written report will capture all safety information including the date of SAE onset, a description of the event, action taken, and an indication whether a relationship between the SAE and drug exists. In addition, a summary of all SAEs that occurred during the previous year, and their outcomes, will be included in the annual progress report to the FDA, NIAAA and our IRB. AEs will be documented at each study visit on the Adverse Event case report form by recording of each adverse event and onset, duration, severity, relation to study medication and any clinical action. These will be compiled and reported to the FDA, NIAAA and our IRB in the annual progress report.

Management of SAEs or Other Study Risks

The study physician will be responsible for managing a drug-related SAE and/or making referrals for appropriate care, as needed, until the problem has resolved or stabilized with no further change expected, or results in death.

DSM Plan Administration

Responsibility for data and safety monitoring

The P.I. is responsible for monitoring this single-site human laboratory trial. [name] will meet with members of her staff and the Study Safety Monitor, [name], on a weekly basis to discuss progress of the study, subject enrollment and retention, the clinical status of active subjects and any safety issues as they arise.

Frequency of DSM

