All case report form data will be entered into an electronic file daily as they are completed. Data safety monitoring will be conducted by the P.I. and Safety Monitor who will review adverse events on a weekly basis. The Safety Monitor will advise the P.I. and the study physicians if any changes in the study plan may be needed to improve subject safety.

Data safety and monitoring reports will be provided annually to the IRB, NIAAA and the FDA. We will use pre-established criteria and procedures for reporting AEs, SAEs, issues potentially arising from conflicts of interest, significant protocol changes, and/or cause for trial termination to the IRB, NIAAA and the FDA.

DSM board plan

Per NIAAA guidelines, no DSM board is required for this single-site, early Phase 2 proof-of-concept study.

23.2 *Has a data and safety monitoring committee been set up for this study?

Yes No

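### As worded, the safety suspension rule is triggered by one Grade 4 treatment-related SAE but not by a treatment-related death

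*Protocol*

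**What the plan says.** The rule was added to the study at the FDA's request and appears in the IRB Summary of Amendments, under the amendment approved 12/09/2020. It is introduced with "Criteria to temporarily suspend the study have been established when either of the following specific safety thresholds are met". The two thresholds are:

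- "One participant with a Common Terminology Criteria for Adverse Events (CTCAE) Grade 4 treatment related SAE"; or
- at least two "participants with a CTCAE Grade 3 treatment related SAE".

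The consequence follows in the same amendment: "If the safety threshold is met, the independent Medical Safety Monitor along with a panel of qualified experienced physicians will meet". The panel makes a recommendation on continuation, and the Principal Investigator sends it to the FDA "within 2 days of receipt of the recommendation from the panel".

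The other relevant text is in Protocol section 23.1:

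- *Collection and Reporting of AEs and SAEs*: if an SAE occurs, the P.I. "will report it to the Scripps-IRB, our NIAAA Project Officer and the US FDA within 48 hours of becoming aware of the event".
- *Management of SAEs or Other Study Risks*: the study physician manages a drug-related SAE "until the problem has resolved or stabilized with no further change expected, or results in death".
- *Frequency of DSM*: adverse events are reviewed weekly, and "The Safety Monitor will advise the P.I. and the study physicians if any changes in the study plan may be needed".
- *DSM board plan*: there is no DSM board.

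The SAP extract contains no stopping or suspension rule.

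**The concern.** Each limb of the rule names a single grade. The first asks for Grade 4 and does not say that a higher grade also counts. In the second, the at-least sign applies to the number of participants, not to the grade. Death appears in neither. Read literally, the rule does not increase with severity: a Grade 4 SAE suspends the study, and a more severe outcome from the same drug need not.

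What is at stake is the automatic response to the worst outcome. With no DSM board, the panel is the only body the supplied text convenes specifically to recommend whether the study continues, and it meets only when the threshold is met. The recommendation that goes to the FDA depends on the same condition. Protocol section 34.1 says that too few people had been studied to identify adverse events specific to the drug, so the rule should not need interpretation at this point. None of this suggests that a death is likely.

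**Working it through.** The plan gives no figure to reproduce. The check is of the rule's logic.

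**Inputs**

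- Limb 1 (IRB Summary of Amendments, approved 12/09/2020): one participant, Grade 4, treatment-related SAE.
- Limb 2 (same place): two or more participants, Grade 3, treatment-related SAE.
- Either limb is enough for suspension, and the panel depends on the same condition.
- Assumption: a fatal event is graded above 4.

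**Notation.** Count participants by their worst treatment-related SAE: *a* at Grade 3, *b* at Grade 4, *c* above Grade 4.

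- As written: suspend if *b* ≥ 1 or *a* ≥ 2.
- Fix A, limb 1 extended upward: suspend if *b* + *c* ≥ 1 or *a* ≥ 2.
- Fix B, both limbs extended upward: suspend if *b* + *c* ≥ 1 or *a* + *b* + *c* ≥ 2.

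**Step 1: one death and nothing else.** (*a*, *b*, *c*) = (0, 0, 1). As written, *b* = 0 and *a* = 0, so 0 of 2 limbs are met and there is no suspension. Under Fix A, *b* + *c* = 1, so limb 1 is met.

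**Step 2: enumeration.** Take *a* = 0 to 2, *b* = 0 to 1 and *c* = 0 to 2, which gives 3 × 2 × 3 = 18 combinations. The written rule and Fix B disagree in 4:

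| *a* (Grade 3) | *b* (Grade 4) | *c* (above 4) | As written | Fixed |
|---|---|---|---|---|
| 0 | 0 | 1 | no | yes |
| 0 | 0 | 2 | no | yes |
| 1 | 0 | 1 | no | yes |
| 1 | 0 | 2 | no | yes |

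Two deaths do not trigger the written rule either. The gap is exactly *c* ≥ 1, *b* = 0 and *a* ≤ 1.

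**Step 3: is limb 1 alone enough?** Fixes A and B could differ only where *b* + *c* = 0. There *a* + *b* + *c* = *a*, so the second conditions are identical. The two fixes therefore agree for any counts, including every combination possible with the planned 50 participants (Protocol section 37.5).

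**Step 4: does the fix add other suspensions?** With *c* = 0, Fix A reduces to *b* ≥ 1 or *a* ≥ 2, which is the written rule. Nothing changes unless an event above Grade 4 occurs.

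**Step 5: does other text close the gap?** The 48-hour requirement is a reporting duty. The weekly review leads to advice. The SAE management text foresees death but attaches no suspension step. Section 23.1 (*Frequency of DSM*) also mentions pre-established criteria covering cause for terminating the trial, but that sentence concerns reporting and states no trigger.

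**Range over the assumption.** If a death is recorded as Grade 4, or the stated grades are taken as minimums, one death already meets 1 of 2 limbs and there is no gap.

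**The case against.** The strongest reply is that a threshold is ordinarily something to meet or exceed, so a sensible reader would treat Grade 4 as a minimum and suspend after a death. Nothing in the documents suggests the team would carry on. The premise that a death is graded above 4 is also not in the documents. The rule is visible only in an amendment summary. The operative IND and amended application are not supplied, apart from the statistical extract, and they may be worded correctly.

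A death would also not go unnoticed. The IRB, NIAAA and the FDA would hear within 48 hours, study physicians and the Safety Monitor take part in ongoing review, emergency unblinding is available, and nothing prevents the P.I. from suspending on other grounds.

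Much of this stands. The slip is probably unintended, physician review would take place in some form, and the practical consequence is modest. What does not follow is that the rule is adequate as written. The safeguards listed are reporting or discretionary steps, and none of them suspends the study or convenes the panel. The usual caution about amendment logs does not apply either: this is the rule that was added, not text that was replaced, and it appears nowhere else in the supplied documents.

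**Conclusion.** The concern holds. Followed literally, the rule omits a treatment-related death when there is no Grade 4 SAE and at most one Grade 3 SAE: 0 of 2 limbs are met as written, and 1 of 2 after the correction. This describes how the rule behaves. It is not a probability, and the documents give no basis for one.

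The conclusion rests on a fatal event being graded above 4 and on the stated grades being read as exact. Confidence is medium because the full IND wording has not been seen. The point affects no estimate or analysis, but it should be corrected because it concerns the most serious safety outcome and the correction is trivial.

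**What to change.** In the first limb, replace Grade 4 with *Grade 4 or higher (including fatal)*. Leave the second limb alone, because any event above Grade 3 then meets the first. Check the full IND text first. If it already says this, bring the summary into line with it.

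The cost is a one-clause amendment with notification to the IRB and the FDA. No participants, procedures or analyses are added, and no suspension is added unless an event above Grade 4 occurs.
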